10.3.2. Treatment Group Comparability

10.3.2.1. Patient Disposition

Frequency counts and percentages of all patients entered, randomized/enrolled, completing Weeks 36 and/or 52, and/or discontinuing from the study and/or study treatment early will be presented for each treatment. The reasons for discontinuation from the study will be summarized by treatment group. Patient disposition will be listed.

10.3.2.2. Patient Characteristics

Demographic and baseline characteristics will be summarized by treatment. For continuous measures, summary statistics will include sample size, mean, median, maximum, minimum, and SDs along with an analysis of variance (ANOVA) p-value to test overall treatment effect. For categorical measures, summary statistics will include sample size, frequency, and percent. Demographics will be summarized for the ITT, Completers, and PP populations.

10.3.2.3. Concomitant Therapy

The prespecified concomitant medications of interest will be summarized by treatment.

Incidence of initiation of rescue therapy for severe, persistent hyperglycemia will be analyzed as an exploratory safety endpoint.

10.3.2.4. Treatment Compliance

Treatment compliance is defined as taking at least 75% of required injections for the visit intervals (see Section 7.6). Overall compliance is defined as being at least 75% compliant with investigational product for at least 75% of visits across the Treatment Period. Compliance will be summarized by each treatment, and overall.

10.3.3. Efficacy Analyses

10.3.3.1. Primary Analyses

There will be 2 primary estimands to compare each investigational dulaglutide dose and dulaglutide 1.5 mg in terms of the primary measure of HbA1c change from baseline to Week 36. See Section 10.3.1.

Both estimands will use the same primary analysis model by employing the MMRM described in Section 10.3.1 in the ITT Population, and each will be tested at the full significance level of 0.05. For each type of estimand, the 2 investigational doses will each be tested versus dulaglutide 1.5 mg simultaneously, controlling the 2-sided alpha of 0.05.

10.3.3.1.1. Secondary Analyses for Primary Endpoint

The primary analysis model, MMRM, will be repeated using the PP Population and the Completers Population to check the sensitivity of the analysis. If the conclusion differs from that of the primary analysis, the data and analyses may be further investigated.

10.3.3.1.2. Multiple Imputation for Missing Data

To investigate departure from the missing at random (MAR) assumption for the primary analysis (MMRM) and check the robustness of the conclusions drawn from the primary analysis, a pattern-mixture model (PMM) coupled with multiple imputation, recommended by National Research Council ([NRC]; 2010), will be performed.

All data including those collected after rescue and/or treatment discontinuation will be included in the analyses. The missing data will be imputed based on measurements from patients in the same treatment arm who discontinued treatment but still had their measurements taken at the primary endpoint visit (Week 36) if there are an adequate number of observations for imputation. An ANCOVA model will be fit to the complete datasets at Week 36, containing effects for treatment, pooled country, and the baseline as a covariate.

Inference based on PMM does not involve directly making the assumption of MAR. Instead, PMM involves making other types of (untestable) identifiability assumptions for the unobservable distributions. This assumption cannot be validated from the observed data. The PMM model depends on the probability mass function of possible missing data patterns, which would not be known a priori. The proposed multiple imputation may require posthoc changes after database lock to resolve any convergence issues.

10.3.3.2. Analyses for Secondary Efficacy Endpoints

The key secondary measures change from baseline to 36 weeks in body weight and FSG, will be analyzed using both models, the MMRM and the ANCOVA, described in Section 10.3.1.

For percentages of patients achieving target HbA1c of <7.0% (53 mmol/mol), longitudinal logistic regression with repeated measurements will be used. The model will include independent variables treatment, pooled country, visit, treatment-by-visit, and baseline HbA1c as a covariate.

Treatment-regimen estimands using an ANCOVA model coupled with a PMM may be conducted for each key secondary continuous endpoint.

10.3.3.3. Multiplicity Adjustments for the Primary and Key Secondary Endpoints Analyses

Superiority for the primary and secondary endpoints for each type of estimand will be assessed in a graphical approach (Bretz et al. 2009; Bretz et al. 2011) to control the overall Type 1 error rate. The tested hypotheses are superiority of each of the investigational dulaglutide doses versus dulaglutide 1.5 mg at Week 36 for the following measures: (1) change from baseline in HbA1c, (2) change from baseline in body weight, (3) percent to target HbA1c <7.0% (53 mmol/mol), and (4) change from baseline in FSG.

Each estimand will be tested at the full significance level of 0.05 (2-sided).

10.3.3.4. Tertiary/Exploratory Efficacy Endpoints

The analysis of patients reaching HbA1c target $\leq 6.5\%$ and other binary outcomes will use the same model as that for HbA1c target <7.0% (53 mmol/mol) described in Section 10.3.3.2.

Longitudinal continuous variables will be analyzed using MMRM described in Section 10.3.1. The analysis will be conducted for on-treatment without rescue medication data. Log-normal-distributed data such as fasting glucagon may be analyzed using log scale.

Nonlongitudinal continuous variables such as 6-point SMPG, HOMA2-IR, and HOMA2-%B will be analyzed using LOCF by fitting a linear model with pooled country, treatment, baseline HbA1c strata as fixed effects, and corresponding baseline value as a covariate. Data transformation may be applied if data are not normally distributed.

10.3.4. Safety Analyses

The safety endpoints will include incidence of AEs, adjudicated AEs, discontinuations due to AEs, SAEs, and TEAEs (defined as postbaseline events that are new events or preexisting conditions that worsened in severity after randomization), hypoglycemic and hyperglycemic episodes, and laboratory analytes. Unless otherwise specified, the ITT Population will be used for analyses of safety measures.

10.3.4.1. Study Drug Exposure

Exposure will be calculated for each patient and summarized by each treatment group.

10.3.4.2. Adverse Events

Adverse events will be coded from the actual term using the Medical Dictionary for Regulatory Activities (MedDRA) and reported with preferred terms and system organ class (SOC). Selected notable AEs of interest may be reported using high-level terms.

Summary statistics will be provided for overall AE, TEAEs, SAEs, study discontinuation due to AEs or death, and study drug discontinuation due to AEs. Counts and proportions of patients experiencing AEs will be reported for each treatment.

Summaries (if appropriate) of adverse events of special interest (AESI) defined in Section 9.2.2 will be generated.

10.3.4.3. Hypoglycemic Episodes

Section 9.2.2.2 contains definitions of categories of hypoglycemia. Summary reports on-treatment without rescue medication will include both incidence and rates of hypoglycemia. Hypoglycemia will be analyzed as documented symptomatic, asymptomatic, nocturnal documented symptomatic, or severe.

Hypoglycemic episodes will be analyzed using 2 hypoglycemic thresholds: Level 1 (glucose alert level, ≤ 70 mg/dL [3.9 mmol/L]) and Level 2 (clinically significant hypoglycemia level, < 54 mg/dL [3.0 mmol/L]). Other categories, including the categories above defined with different glucose thresholds, may also be included in these analyses when deemed appropriate.

The incidence will be analyzed using the categorical methods described in Section 10.3.1 and rate of hypoglycemic episodes (events/patient/1 year) will be analyzed using a generalized linear mixed-effects model assuming negative binomial distribution for hypoglycemic episodes if data warrants. Otherwise, the rate will be analyzed using Wilcoxon rank-sum test. Incidence and rates will be summarized for each treatment arm and entire Treatment Period.

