3.3. Benefit/Risk Assessment

More information about the known and expected benefits, risks, serious adverse events (SAEs) and reasonably anticipated AEs of dulaglutide may be found in the Investigator's Brochure (IB).

In addition, detailed information about the known and expected benefits and risks of dulaglutide may be found in the Trulicity USPI (2017 [WWW]) and SmPC (2017 [WWW]).

4. Objectives and Endpoints

Table GBGL.1 presents the objectives and endpoints of the study.

Table GBGL.1. Objectives and Endpoints

Objectives	Endpoints

Primary To demonstrate that once weekly dulaglutide 4.5 mg and/or 3.0 mg is superior to dulaglutide 1.5 mg for change from baseline in HbA1c at 36 weeks in patients with inadequately controlled T2D on concomitant metformin therapy.
	
 • The change in HbA1c from baseline

Secondary Efficacy: To demonstrate that once weekly dulaglutide 4.5 mg and/or 3.0 mg is superior to dulaglutide 1.5 mg for secondary efficacy parameters at 36 weeks (controlled for Type 1 error).
 
Safety: To compare each investigational dulaglutide arm (4.5 mg, 3.0 mg) to the 1.5 mg arm for selected safety parameters through 36 and 52 weeks (unless noted otherwise)
 
Pharmacokinetics (PK) and Pharmacodynamics (PD): To characterize dulaglutide PK and the dose and/or exposure-response relationships for key efficacy (eg, HbA1c and weight), and safety (eg, heart rate [HR]) endpoints.
	
 • The change in body weight from baseline • Proportion of patients achieving HbA1c target <7.0% (53 mmol/mol) • The change in fasting serum glucose (FSG) from baseline • Incidence of treatment-emergent adverse events (TEAEs) and discontinuation of study drug due to adverse events (AEs) • Adjudicated and confirmed cardiovascular and pancreatic AEs • Incidence of thyroid neoplasm AEs • Incidence of treatment-emergent (TE) dulaglutide anti-drug antibodies (ADA) and systemic hypersensitivity reactions • Change from baseline in pulse rate (PR) • Electrocardiogram (ECG) parameters • Occurrence of hypoglycemic episodes • PK parameters (eg, maximum concentration [C_{max}], area under the curve [AUC]) at steady state • Pharmacodynamic evaluations may include changes from baseline in HbA1c, body weight, and heart rate at Weeks 36 and 52

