- **Severe hypoglycemia** is defined as an episode requiring the assistance of another person to actively administer carbohydrate, glucagon, or other resuscitative actions. These episodes may be associated with sufficient neuroglycopenia to induce seizure or coma. Plasma glucose measurements may not be available during such an event, but neurological recovery attributable to the restoration of PG to normal is considered sufficient evidence that the event was induced by a low PG concentration.

Other hypoglycemia categories:

- **Nocturnal hypoglycemia** is defined as any hypoglycemic event that occurs between bedtime and waking.
- **Relative hypoglycemia** is defined as any symptomatic event during which the person reports any of the typical symptoms of hypoglycemia and interprets those as indicative of hypoglycemia, but a measured PG concentration > 70 mg/dL (> 3.9 mmol/L) is collected.
- **Probable symptomatic hypoglycemia** is defined as symptoms of hypoglycemia but PG measurement was not reported.

All reported cases of hypoglycemia will be reported on the hypoglycemia eCRF.

To avoid duplicate reporting, all consecutive PG values ≤ 70 mg/dL (3.9 mmol/L) occurring within a 1-hour period may be considered to be a single hypoglycemic event (Weinberg et al. 2010; Danne et al. 2013).

In each case of suspected or confirmed hypoglycemia, it is important that details for each event be recorded on the eCRF as completely and accurately as possible, including information on the date, time, PG value, symptoms, and the nature and outcome of any interventions. The role of dietary changes and physical exercise (or any other contributing factor) in the development of an event should be established. The patient should receive additional education, if deemed appropriate. Management of increased risk of hypoglycemia is described in Section 7.7.1 and Section 8.1.1.

It is important that each case of suspected or confirmed hypoglycemia be properly categorized with respect to severity. **If a hypoglycemic event meets the criteria of severe, it also needs to be recorded on the AE eCRF as serious and reported to Lilly as an SAE.**

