10.3. Statistical Analyses

10.3.1. General Statistical Considerations

Statistical analysis of this study will be the responsibility of Eli Lilly and Company or its designee. Any change to the data analysis methods described in the protocol will require an amendment ONLY if it changes a principal feature of the protocol. Any other change to the data analysis methods described in the protocol, and the justification for making the change, will be described in the statistical analysis plan (SAP) or the clinical study report (CSR). Additional exploratory analyses of the data may be conducted as deemed appropriate.

Table GBGL.4 defines the populations to be used for analyses.

Efficacy and safety analyses will be conducted in the Intent to Treat (ITT) Population. There will be 2 primary estimands to compare treatment groups in terms of the primary measure of HbA1c change from baseline to Week 36.

One primary estimand will be an efficacy estimand (*de jure* effect) which will use the data collected before initiation of any rescue medication or premature treatment discontinuation to demonstrate the effect of treatment and avoid confounding effects of other antihyperglycemic agents (Little and Kang, 2014). The other primary estimand will be a treatment-regimen estimand (*de facto* effect) which will include data collected after initiation of other antihyperglycemic therapy and/or after premature treatment discontinuation.

The treatment-regimen (*de facto*) estimand is included as primary at the request of the US Food and Drug Administration (FDA). The efficacy (*de jure*) estimand will be considered primary for all other purposes, and will be applied to all efficacy outcomes unless otherwise specified to demonstrate effect of treatment and avoid confounding effects with other antihyperglycemic agents.

Both estimands will be tested at the full significance level of 0.05.

Analyses of safety parameters, except for hypoglycemia events, will be conducted in the ITT Population unless otherwise specified.

Unless otherwise noted, all tests of treatment effects will be conducted at a 2-sided alpha level of 0.05, and CIs will be calculated at 95%, 2-sided. All tests of interactions between treatment groups and other factors will be conducted at a 2-sided alpha level of 0.10.

The baseline will be at the randomization visit (Visit 3). If baseline data are missing, the last nonmissing measurement taken prior to Visit 3 will be used.

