6.10.1.2.2. Hypoglycemia and Hyperglycemia

The rescue therapy definition in this section is based on the response in the CRF noting rescue therapy for severe, persistent hyperglycemia, which differs from “on-treatment with rescue,” as defined in Section 6.1.

6.10.1.2.2.1. Hypoglycemic Episodes

Detailed definitions for various categories of hypoglycemia are defined in the protocol (GBGL Protocol Section 9.2.2.2). For analyses purposes, the following main categories of hypoglycemia will be considered:

- **Documented symptomatic hypoglycemia** is defined as any time a patient feels that he/she is experiencing symptoms and/or signs associated with hypoglycemia, and has a documented plasma glucose (PG) level below the defined threshold.
- **Severe hypoglycemia** is defined as an episode requiring the assistance of another person to actively administer carbohydrate, glucagon, or other resuscitative actions. These episodes may be associated with sufficient neuroglycopenia to induce seizure or coma. Plasma glucose measurements may not be available during such an event, but neurological recovery attributable to the restoration of PG level to normal is considered sufficient evidence that the event was induced by a low PG concentration.
- **Total hypoglycemia** is defined as an episode with PG level below the defined threshold, regardless of symptoms, an episode of symptomatic hypoglycemia where PG level was not measured (ie, probable), and all severe hypoglycemia episodes.

Analyses of total and documented symptomatic hypoglycemia will include categories defined based on 2 PG cutoffs: PG ≤ 70 mg/dL (3.9 mmol/L) cutoff (Glucose Alert Level 1) and PG < 54 mg/dL (3.0 mmol/L) cutoff (Glucose Alert Level 2) (International Hypoglycaemia Study Group 2017). Per American Diabetes Association and European Association for the Study of

Diabetes recommendations, Glucose Alert Level 2 is considered clinically important hypoglycemia for reporting in results of clinical trials of glucose-lowering drugs. Analysis of hypoglycemia episodes with a PG ≤ 70 mg/dL (3.9 mmol/L) also will be included for comparability to prior studies in the dulaglutide development program.

In the analyses described above, hypoglycemia data will be censored at the time of receipt of rescue medication.

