Additionally, a separate analysis will report all hypoglycemia events with PG < 54 mg/dL (3.0 mmol/L), regardless of symptoms, and all severe hypoglycemia episodes for the Safety Population including events that occurred after patients started new antihyperglycemic medications (including rescue medications). In recent regulatory interactions, FDA indicated that Level 2 hypoglycemia (PG < 54 mg/dL or PG < 3 mmol/L) represents a clinically meaningful degree of hypoglycemia and should be summarized as part of study results.

To avoid duplicate reporting, all consecutive PG values ≤ 70 mg/dL (3.9 mmol/L) occurring within a 1-hour period may be considered to be a single hypoglycemic event (Weinberg et al. 2010; Danne et al. 2013).

For each of the hypoglycemia categories, the incidence will be analyzed using the methods for analyses of categorical data described in Section 6.1, by randomized treatment. The rate of hypoglycemic episodes will be analyzed using a generalized linear mixed-effects model assuming negative binomial distribution for hypoglycemic episodes with pooled country and treatment as fixed effects and baseline HbA1c as covariate. The logarithm of days during active treatment period will be adjusted as an offset to account for possible unequal treatment duration between patients. This model will be implemented using SAS[®] procedure GLIMMIX using the log-link function. The predicted hypoglycemia rate per 1 year by treatment will also be presented. For rare hypoglycemic episodes such as severe hypoglycemia, Wilcoxon rank sum test will be used to compare the corresponding 1-year hypoglycemia rates between each investigational dulaglutide dose and dulaglutide 1.5 mg.

6.10.1.2.2.2. Severe, Persistent Hyperglycemia

Summaries (if appropriate) will be provided for patients initiating rescue therapy for events of severe, persistent hyperglycemia by each randomized treatment. The time to initiation of rescue therapy for severe, persistent hyperglycemia will be analyzed using PROC LIFETEST to generate Kaplan-Meier curves for each treatment. The summary reports including Kaplan-Meier curves will only be generated if $\geq 1\%$ of patients receive rescue intervention.

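### The SAP replaces the protocol's separate asymptomatic and nocturnal documented symptomatic hypoglycemia analyses with a pooled total category and gives no reason

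*Protocol*

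**What the plan says.** Protocol 10.3.4.3 states: "Hypoglycemia will be analyzed as documented symptomatic, asymptomatic, nocturnal documented symptomatic, or severe". It asks for incidence and rates by treatment arm, using two thresholds (<=70 and <54 mg/dL). Only further categories beyond these are optional.

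Protocol 9.2.2.2 defines documented asymptomatic hypoglycemia at both levels. It also defines nocturnal hypoglycemia, which "is defined as any hypoglycemic event that occurs between bedtime and waking". In the table of objectives and endpoints (Protocol Section 4), "Occurrence of hypoglycemic episodes" is a secondary safety endpoint.

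SAP 6.10.1.2.2.1 begins its list with "For analyses purposes, the following main categories of hypoglycemia will be considered" and gives documented symptomatic, severe and total. Total hypoglycemia "is defined as an episode with PG level below the defined threshold, regardless of symptoms"; it also takes in symptomatic episodes with no glucose measurement and all severe episodes. On thresholds, "Analyses of total and documented symptomatic hypoglycemia will include categories defined based on 2 PG cutoffs". For each SAP category, "the incidence will be analyzed using the methods for analyses of categorical data described in Section 6.1, by randomized treatment". Rates use a negative binomial model, with a Wilcoxon test for rare episodes. A further analysis pools every event below 54 mg/dL with all severe events, including those after new antihyperglycemic medication.

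On changes that are not principal features, Protocol 10.3.1 says: "Any other change to the data analysis methods described in the protocol, and the justification for making the change, will be described in the statistical". The rest of that sentence allows either of two places for this, the SAP or the clinical study report.

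**The concern.** The protocol's wording for the four categories is a commitment, and two of them have no analysis of their own in the SAP. The SAP refers to the protocol for detailed definitions but applies its by-treatment methods to its own list.

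The silence is notable because the SAP explains other departures from the protocol. Section 6.1.2.1 says why the retrieved-dropout definition differs, and Section 6.9.2.2 says which planned MMRM analyses will not be done and what replaces them. The only hypoglycemia analysis entry in the revision history (SAP Section 3) records an addition.

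At stake is whether a reader of the study report can see how episodes without symptoms, and symptomatic episodes at night, compare between 4.5 mg or 3.0 mg and 1.5 mg. The protocol set both out for analysis before any data were seen.

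**Working it through.** There is no planned figure to reproduce. The check sets the two lists side by side and asks what the SAP tables allow a reader to derive.

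**1. Category lists** (Protocol 10.3.4.3 against SAP 6.10.1.2.2.1)

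| Category | Protocol | SAP |
|---|---|---|
| Documented symptomatic | yes, two thresholds | yes, two thresholds |
| Asymptomatic | yes, two thresholds | only inside pooled groups |
| Nocturnal documented symptomatic | yes, two thresholds | not mentioned; falls inside documented symptomatic |
| Severe | yes | yes |
| Total | not listed | yes, two thresholds |

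Severe hypoglycemia is defined by the need for assistance, not by a glucose value, so the thresholds do not apply to it.

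**2. Count**

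- Protocol: 3 categories x 2 thresholds + 1 severe = 7 sets of results.
- Kept separately in the SAP: 1 x 2 + 1 = 3.
- Not kept separately: 7 - 3 = 4, that is, 2 categories x 2 thresholds.
- With incidence and rate for each, 4 x 2 = 8 summaries.

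**3. Are any events left out of every comparison?** No. An asymptomatic episode below the threshold counts in the total. A nocturnal documented symptomatic episode counts in both documented symptomatic and total. Both SAP categories are compared by randomized treatment.

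**4. Can asymptomatic episodes be recovered from the tables?** At one threshold, count episodes as follows: S documented symptomatic, A documented asymptomatic, U documented with symptoms unspecified, P probable (no glucose value), and V severe episodes not already in S, A or U. Then:

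- T (total) = S + A + U + P + V
- T - S = A + U + P + V

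U and P have no table of their own. Severe episodes do, but their overlap with the other groups is not shown. The tables therefore give only 0 <= A <= T - S. Patient incidence is less recoverable still, because a patient with both symptomatic and asymptomatic episodes is counted once in the total.

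The additional <54 mg/dL analysis does not help. It leaves out P but still mixes A with S and U. It also includes events after rescue, while the main categories are censored there, so the two cannot simply be subtracted.

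**5. Can nocturnal documented symptomatic episodes (N) be recovered?** They are a subset of S and nothing splits S by time of day. Only 0 <= N <= S follows.

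**The case against.** The strongest reply is that no event is lost. The total category includes every asymptomatic episode below the threshold, documented symptomatic includes the nocturnal ones, and both are compared by dose for incidence and rate. The endpoint is the occurrence of hypoglycemic episodes, not divided by symptoms or time of day, and a pooled total answers it more directly than the protocol's list, which had none. The SAP calls its categories the main ones and allows additional analyses (Section 6.1), so it does not rule the other two out. All of this stands. A reader might infer that these episodes are never compared by dose, or that the secondary endpoint is lost; the documents support neither.

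A reader might also infer a breach of the rule on justifying changes. They do not support that either: Protocol 10.3.1 and SAP 6.1 both let the reason appear in the clinical study report. The revision history covers only key changes in Version 2.0, and Version 1.0 is not available here, so it cannot show when the two categories were left out.

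Two further arguments should not be used. One is that pooling must hide a dose effect. The documents give no event rates, and pooling weakens a comparison or strengthens it depending on whether the other episodes also vary with dose. The other is that asymptomatic lows depend least on patient reporting. Protocol 5.1 says routine self-monitored readings serve only to guide glucose management, and under Protocol 9.2.2.2 episodes reach the eCRF through the patient's diary.

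The reply does not restore the separate comparisons. Permission to add analyses, even after database lock, is weaker than a prespecified commitment. SAP 6.1 allows analyses to be skipped only where they relate to exploratory objectives, and hypoglycemia is listed under the secondary ones.

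**Conclusion.** The protocol and SAP conflict on prespecified safety comparisons. Two of four protocol categories, at two thresholds each, have no separate comparison by dose in the SAP, cannot be derived from its planned tables, and are left out without explanation.

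This is a minor consistency correction. It concerns the breakdown of a secondary safety endpoint and leaves efficacy conclusions, alpha control and sample size untouched. Counts may be small, since Protocol 7.7.5.2 expects no clinically relevant increase in hypoglycemia risk.

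The conclusion rests on reading the SAP's list as the set to which its methods apply. It also assumes that no separate output plan, unseen here, adds the two categories.

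**What to change.** In SAP 6.10.1.2.2.1, add documented asymptomatic and nocturnal documented symptomatic hypoglycemia as analysis categories at <=70 and <54 mg/dL. Use the incidence and rate methods already given there, with the Wilcoxon test where episodes are rare, and the same censoring at rescue as the other main categories. Keep the total category and the additional <54 mg/dL analysis.

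If the sponsor intends to drop the two categories, say so in the same section, with the reason, before database lock. The protocol would accept an explanation in the study report, but one written before results are known carries more weight.

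The cost is a few extra safety tables, at most the 8 summaries counted above, some perhaps with few events. No new data collection should be needed. Protocol 9.2.2.2 already has date, time, glucose value and symptoms recorded for each episode, and asks investigators to categorize episodes by its definitions, including nocturnal. The form itself is not in the documents, so confirm that it identifies events between bedtime and waking.
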